4 PATIENTS EVALUABILITY CRITERIA

The study population will include the following analysis sets definitions:

- “All Included Patients” analysis set is defined as all patients recorded in the database who have been included in the trial, regardless of whether they have received the study drug or not.
- “All Treated Patients” analysis set is defined as all included patients who have received any partial or complete infusion of PM01183.
- “All Evaluable Patients” analysis set is defined as all eligible patients, defined as patients accepted by the sponsor to take part in the trial, who have had at least one complete infusion of PM01183, and either have had at least one assessment (as per RECIST v1.1) or have been categorized as “treatment failures”. Patients who discontinue treatment due to any treatment-related toxicity before an appropriate tumor assessment has been performed or those who experience early death due to malignant disease or those with treatment withdrawn due to clinical PD/symptomatic deterioration with no tumor assessments will be defined as “treatment failures”. These patients will be included as non-evaluable for response in the analysis of objective response as per RECIST v1.1, although they will not be replaced as will be considered evaluable for efficacy. For the IRC assessment in SCLC patients same definition will be followed but based on its assessment.
- “All Responding Patients” analysis set is defined as all evaluable patients who have had a confirmed CR or PR as overall best response according to the RECIST v1.1. For the IRC assessment in SCLC patients same definition will be followed but based on its assessment.

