5.3 REPLACEMENT OF PATIENTS

Patients will be replaced if they are not evaluable for the primary endpoint of the study (ORR as per RECIST v. 1.1), specifically if (any of the following):

- They are not eligible.
- They have not received the study treatment.
- They are not evaluable for ORR as per RECIST v1.1 and they are not categorized as “treatment failures”. Treatment failures will not be replaced and are defined as patients who:
 - o Discontinue treatment due to any treatment-related toxicity before an appropriate tumor assessment has been performed.
 - o Early death due to malignant disease.

All replaced patients who received study treatment will be included in the safety analysis.

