6.6 DOSE REDUCTION

Patients may continue the study treatment at a reduced dose if they present any of the following:

- Grade ≥ 3 treatment-related non-hematological toxicity. Exceptions are: grade ≥ 3 nausea and/or vomiting not optimally treated, grade 3 asthenia lasting ≤ 3 days, grade 3 diarrhea lasting ≤ 2 days or not optimally treated, grade 3 transient ALT/AST elevations which are rapidly reversible and not leading to subsequent delays, and non-clinically relevant biochemical abnormalities.
- Grade 4 thrombocytopenia or grade 3 thrombocytopenia concomitantly with grade ≥ 3 bleeding.
- Grade 4 neutropenia, any grade febrile neutropenia or neutropenia associated with infection/sepsis.
- Frequent or prolonged (>1 week) dose delays due to treatment-related adverse events.

Patients who experience grade 3/4 hypersensitivity reactions will be discontinued from study treatment.

Dose reduction levels are shown in [Table 7](#).

Table 7. Criteria for dose reduction.

Dose reduction	PM01183 dose (mg/m ²) *
1 (starting dose)	3.2 **
-1	2.6
-2	2.0

*Dose rounded to the first decimal.

**Dose will be capped at BSA of 2.0 m² (i.e., dose will not exceed 6.4 mg).

BSA, body surface area; ECOG, Eastern Cooperative Oncology Group; PS, performance status.

Up to two dose reductions are allowed per patient.

Patients who continue to experience treatment-related toxicity and/or frequent dose delays after permitted dose reductions must be withdrawn from the study. They can continue receiving the study medication if objective clinical benefit is adequately documented by the Investigator, and upon agreement with the Sponsor. Once the dose has been reduced for an individual patient, it will not be re-escalated under any circumstances.

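### The SAP's evaluable set requires one complete infusion, so a patient whose only infusion is abandoned for toxicity before any scan leaves the primary ORR denominator, although Protocol 5.3 keeps that patient as a treatment failure.

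*SAP*

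**What the plan says.** **SAP 4, All Evaluable Patients.** The set consists of eligible patients "who have had at least one complete infusion of PM01183, and either have had at least one assessment" under RECIST or been classed as treatment failures. The infusion condition comes first and is joined by *and*, so it governs both branches.

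**SAP 4, treatment failures (same paragraph).** The toxicity limb reads "Patients who discontinue treatment due to any treatment-related toxicity before an appropriate tumor assessment has been performed" and carries no infusion condition of its own. Treatment failures are entered as non-evaluable for response, "although they will not be replaced as will be considered evaluable for efficacy".

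**SAP 4, All Treated Patients.** This set is "all included patients who have received any partial or complete infusion of PM01183".

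**Protocol 5.3.** "Treatment failures will not be replaced and are defined as patients who" meet either of two criteria, one of which is "Discontinue treatment due to any treatment-related toxicity before an appropriate tumor assessment has been performed". No minimum infusion is set. The only exposure ground for replacement is "They have not received the study treatment".

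**Use of the sets (SAP 4.2 and 6.1).** All Evaluable is the primary ORR set in every cohort except SCLC, with All Treated as a sensitivity analysis. In SCLC the roles are reversed.

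**The concern.** A patient whose first infusion is abandoned for a drug reaction, and who is then taken off treatment without a scan, is a treatment failure under Protocol 5.3 and a non-responder in the ORR. Under the opening condition of the SAP definition the same patient is not in the set at all.

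The case can arise under the plan. Protocol 6.6 states: "Patients who experience grade 3/4 hypersensitivity reactions will be discontinued from study treatment". It does not say that such a reaction occurs at the first infusion or leaves it unfinished, so it shows a route and not a frequency.

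Two things are at stake in the eight non-SCLC cohorts. The first is the primary denominator: every patient lost this way is a non-responder, so the reported ORR can only move up. The second is the count of evaluable patients that triggers the look at 15 and fills the targets of 25 and, for endometrial carcinoma, 50 (SAP 5.1 and 8.13).

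**Working it through.** **1. The definitions side by side.** Take an eligible patient with one infusion, permanently stopped partway for related toxicity, and no tumor assessment.

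| Rule | Result |
|---|---|
| Protocol 5.3, treatment failure | Met; no infusion minimum |
| Protocol 5.3, replacement for lack of exposure | Does not apply; some drug was given |
| SAP 4, toxicity limb of treatment failure | Met |
| SAP 4, opening condition of All Evaluable | Not met; no complete infusion |
| SAP 4, closing sentence on treatment failures | Evaluable, not replaced |
| SAP 4, All Treated | Included |

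Only the opening condition excludes the patient. It conflicts with Protocol 5.3 and with the end of its own paragraph. It cannot be put down to loose drafting, because All Treated, defined in the same list, explicitly accepts a partial infusion.

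**2. Effect on the estimate, no replacement.** For x responses among n patients, one of whom is excluded, ORR goes from x/n to x/(n − 1).

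- 25-patient cohort, 3 responses: 3/25 = 12.0% becomes 3/24 = 12.5%.
- 25-patient cohort, 2 responses: 2/25 = 8.0% becomes 2/24 = 8.3%.

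**3. The plan's own endometrial figures.** Inputs from SAP 5.1: n = 50, reject at 10 or more responses, p0 = 0.10, p1 = 0.25, one-sided alpha 0.025.

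- Normal-approximation power: Φ{[(0.25 − 0.10) − 1.96·√(0.10·0.90/50)] / √(0.25·0.75/50)} = 86.2% (stated ~86%).
- Exact power: P(X ≥ 10 | 50, 0.25) = 83.6% (stated ~84%).
- Exact single-stage type I error: P(X ≥ 10 | 50, 0.10) = 0.0245.

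These reproduce. No design figure is wrong because of the definition.

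**4. Effect on the test, no replacement.** Success is a count of responses, and removing a non-responder leaves the count unchanged. To check, hold the overall null rate at 10% and let k of the 50 be certain non-responders. The remaining 50 − k then respond at 0.10/(1 − k/50):

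- k = 1: P(X ≥ 10 | 49, 0.10/0.98) = 0.0244.
- k = 2: P(X ≥ 10 | 48, 0.10/0.96) = 0.0242.

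Against 0.0245 there is no inflation.

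**5. Effect on the test, with replacement.** If the excluded patient were instead treated as non-evaluable and replaced, 10 responses would be sought among more treated patients:

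- One replaced: P(X ≥ 10 | 51, 0.10) = 0.0279.
- Two replaced: P(X ≥ 10 | 52, 0.10) = 0.0315.

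Both exceed 0.025. For the rule of 2 or more among 25 at p0 = 0.01, the single-stage exact error is 0.0258, and 0.0277 with one replaced patient.

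The values of k (1 and 2) are assumptions. The documents give no rate of first infusions abandoned for toxicity.

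**The case against.** The strongest reply is that the effect is close to nothing. The patient must have a first infusion abandoned for good, stop for related toxicity, and have no scan. An infusion that is interrupted and then finished is plausibly complete, and SAP 12.1.4 lists only temporary interruptions. Protocol 1.10.1.3 describes non-hematological toxicity as generally mild and reversible. It names hematological toxicity as the most relevant, with the nadir usually in the second week, when the infusion is already over. Such patients stay evaluable under either document. The All Treated sensitivity analysis will show any difference, Listing 10.1.4 will name each non-evaluable patient with the reason, and the SCLC primary analysis uses All Treated already. All of this stands, and it limits the size of the point. It does not repair the primary set in the other eight cohorts, nor the count of evaluable patients at the interim looks.

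A reader might go further and infer that the SAP definition inflates the type I error. The documents do not support that as a general statement. The inflated figures need replacement of the excluded patient, and Protocol 5.3 and SAP 4 both say treatment failures are not replaced. To reach replacement one must let the opening SAP condition override that sentence and then apply the rule that reopens recruitment for non-evaluable patients (Protocol 3, SAP 2). The paragraph's internal conflict leaves that reading open but does not establish it.

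The single-stage baseline also ignores the earlier futility looks. Applying the endometrial stops at 0 of 15 and fewer than 2 of 25 gives 0.0241 in place of 0.0245.

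**Conclusion.** Wrong as written, minor. The SAP excludes from the primary ORR set of the eight non-SCLC cohorts a patient whom Protocol 5.3, and the SAP's own non-replacement sentence, keep as a non-responder. The bias runs one way: about 0.3 to 0.5 percentage points of ORR for one such patient in a 25-patient cohort with 2 or 3 responses, and zero if none occurs. The conclusion rests on reading *and* literally, as a programmer would. In SCLC only the evaluable-set sensitivity analysis is touched.

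**What to change.** In the All Evaluable definition in SAP 4, replace the requirement of at least one complete infusion with any partial or complete infusion, the wording the SAP already uses for All Treated. All treatment failures defined in Protocol 5.3 then stay in the denominator, count toward the evaluable targets, and are not replaced. The change concerns the analysis set only.

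The cost is one phrase. Reported ORR may be very slightly lower, and no sample size, boundary or table shell has to change.

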10.1 Patient Disposition

Main characteristics concerning inclusion in the study, withdrawal from the study and protocol deviations will be displayed in this section.

Each table, listing and figure will have a comprehensive header identifying the tumor type (cohort) or the total population (if applicable).

Table 10.1.1 Number of patients included, treated and evaluable for the primary endpoint.

	N	%
Included patients		
Eligible patients*		
Treated patients		
Evaluable patients for efficacy**		
Evaluable patients for efficacy by IRC (SCLC cohort)***		

(*) Patients who were considered eligible according to the registration screening form and were accepted to take part in the trial with the sponsor's agreement in the screening reply form. (**) Includes patients treated with early death/or PD not documented by image (early PD). (***) For sensitivity analysis.

Listing 10.1.2 Patients who do not meet all the inclusion criteria.

Patient id.	Criterion number(s) and description

Listing 10.1.3 Patients who meet any exclusion criteria.

Patient id.	Criterion number(s) and description

Listing 10.1.4 Non-evaluable patients for efficacy analysis.

Patient id.	Reason

Listing 10.1.5 Non-evaluable patients for efficacy analysis by IRC (SCLC cohort).

Patient id.	Reason

Listing 10.1.6 Non-evaluable patients for safety (Non-treated patients).

Patient id.	Reason

Table 10.1.7 Patients accrual by institution.

No. of patients included	Country 1		N	%
		Institution 1		
	...			
	Total			
	...	Institution 1		
		...		

	Total	Total		
		Institution 1		
		...		
	Country 1	Total		
		Institution 1		
		...		
No. of patients treated	...	Total		
		Institution 1		
		...		
	Total	Total		
		Institution 1		
		...		

Table 10.1.8 Study dates.

	Total
Date of first registration	
Date of first dose of the first patient	
Date of last registration	
Date of first dose of the last patient	
Date of last dose	
Date of last follow-up*	

(*) Last follow-up, examination or procedure before clinical cut-off or study closure.

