10.2 Reasons for Treatment and Study Discontinuation

Each table, listing and figure displayed in this section will have a comprehensive header identifying the tumor type (cohort) or the total population (if applicable). The reasons for treatment discontinuation will be calculated in the treated patient's population. The rest of tables and listings in this section will be calculated in the included patient's population.

Table 10.2.1 Treatment discontinuation.

Reason	N	%
Progressive disease		
Treatment-related adverse event*		
Non treatment-related adverse event*		
Patient refusal to treatment*		
Death**		
Investigator's decision*		
Other*		
Ongoing at cutoff		
Total		

Note: Also for s1 and s2; (*) Specify (see Listing 10.2.2), (**) Cause of Death (See Table 12.3.2.1).

Listing 10.2.2 Reasons for treatment discontinuation other than progressive disease.

Patient id.	CTFI*	Reason	Last cycle	Comments

(*) Only for SCLC patients (RR, R, S, VS).

Table 10.2.3 Reasons for treatment discontinuation by cycles received.

Reason	Last cycle			
	1	2	...	Total

Progressive disease				
Treatment-related adverse event*				
Non treatment-related adverse event*				
Patient refusal to treatment*				
Death**				
Investigator's decision*				
Other*				
Ongoing at cutoff				
Total				

(*) Specify (see Listing 10.2.2); (**) Cause of Death (See Table 12.3.2.1);

When the reason for discontinuation is a study treatment-related adverse event or study treatment-related death, identify patients and describe them in detail here.

Listing 10.2.4 Treatment discontinuation due to adverse events.

Patient id.	CTFI*	Last cycle	Preferred term code	Adverse event reported (verbatim)	Grade	Relationship	Onset date	Resolved date	Seriousness criteria

(*) Only for SCLC patients (RR, R, S, VS).

Table 10.2.5 Study discontinuation.

Reason	N	%
Never treated*		
Study termination (clinical cut-off)		
Patient's refusal		
Death**		
Lost to follow-up		
Other ***		
Total		

Note: Also for s1 and s2; (*) See Listing 10.2.6; (**) Cause of Death (See Table 12.3.2.1); (***) Specify (see listing 10.2.7).

Listing 10.2.6 Patients included but not treated.

Patient id.	Off-study reason

Listing 10.2.7 Study discontinuation due to other reason.

Patient id.	Specify

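### Treated patients who die before the first scan from a cause neither malignant nor treatment-related (or unknown) leave the evaluable set and are replaced, although they can only be non-responders

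*SAP*

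**What the plan says.** Protocol 5.3 replaces treated patients under this condition: "They are not evaluable for ORR as per RECIST v1.1 and they are not categorized as" treatment failures. It defines treatment failure by two routes: "Discontinue treatment due to any treatment-related toxicity before an appropriate tumor assessment has been performed" and "Early death due to malignant disease". For those who are replaced it names one analysis only: "All replaced patients who received study treatment will be included in the safety analysis".

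SAP 4 builds the All Evaluable set on the same idea. Besides at least one complete infusion, a patient needs a tumor assessment or treatment-failure status. The toxicity route is the same as in the protocol. The death route is "those who experience early death due to malignant disease". The SAP adds a third route that the protocol lacks: "those with treatment withdrawn due to clinical PD/symptomatic deterioration with no tumor assessments". Neither document defines early.

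The footnote to the row for patients evaluable for efficacy in SAP Table 10.1.1 reads "Includes patients treated with early death/or PD not documented by image (early PD". It names early death without a cause.

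Under SAP 4.2 and 6.1, All Evaluable is the primary ORR denominator in every cohort except SCLC, where All Treated is used. In the other cohorts All Treated serves for a sensitivity analysis. Protocol 3, 8.1 and 8.3 state the decision points (15, 25, 50 and 100) in evaluable patients.

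**The concern.** The routes into treatment failure do not cover every way a treated patient can die before imaging. A fatal cardiac event or infection judged unrelated to the drug, or a death of unknown cause, is neither toxicity nor malignant disease, and it is not a withdrawal for clinical progression. The plan expects such deaths: the cause-of-death shell in SAP 12.3.2 has rows for non-drug-related events and for other causes. There is also time for them to occur, because the first scan comes after two three-week cycles (Protocol 6.3 and 7.1).

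A patient who dies before any post-baseline scan cannot have a confirmed response. The gap therefore removes only non-responders, and each removal brings in a replacement with a fresh chance to respond. Whether the patient stays in the denominator depends on a judgement of cause of death in an open-label, single-arm trial. What is at stake is the primary ORR in eight cohorts, the success counts tied to it, and the counts that decide whether a cohort continues.

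**Working it through.** **Step 1. Trace the patient.** A treated patient with no post-baseline assessment:

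| What happened | Protocol 5.3 | SAP 4 |
|---|---|---|
| Stopped for treatment-related toxicity | failure, kept | failure, kept |
| Early death, malignant disease | failure, kept | failure, kept |
| Withdrawn for clinical progression | no route | failure, kept |
| Death, neither malignant nor treatment-related, or unknown | no route, replaced | no route, not evaluable |

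The last row is the gap.

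**Step 2. Reproduce the plan's figures (SAP 5.1).** Endometrial: n = 50, success at 10 or more responses, p0 = 0.10, p1 = 0.25.

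- Exact type I error: P(X ≥ 10 | 50, 0.10) = 0.0245, against the stated 0.025.
- Exact power: P(X ≥ 10 | 50, 0.25) = 83.6%, against the stated ~84%.
- Normal approximation: Φ[(0.15 − 1.96·√(0.10·0.90/50)) / √(0.25·0.75/50)] = Φ[(0.15 − 0.0832)/0.0612] = 86.2%, against the stated ~86%.

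25-patient rule: stop at 0 of 15, success at 2 or more responses, p0 = 0.01. P(success) = P(X₁₅ ≥ 2) + P(X₁₅ = 1)·[1 − (1−p)¹⁰]. At p = 0.01 this is 0.0096 + 0.1303 × 0.0956 = 0.0221. At p = 0.10 it is 67.4%, near the stated ~70%.

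**Step 3. Exclude and replace.** Let d be the share of treated patients in the gap. None of them responds, so a rate p among treated patients becomes p/(1−d) among evaluable patients. The documents give no d. The values below are assumptions, and the null rate is taken to hold among treated patients.

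| d (assumed) | Endometrial rate tested, 0.10/(1−d) | Endometrial type I error | 25-patient rule type I error |
|---|---|---|---|
| 0 | 0.1000 | 0.0245 | 0.0221 |
| 2% | 0.1020 | 0.028 | 0.0229 |
| 4% | 0.1042 | 0.031 | 0.0238 |
| 8% | 0.1087 | 0.041 | 0.0258 |

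The endometrial column is the single-stage calculation at 50 patients and ignores the interim stops.

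**Step 4. One death at the endometrial boundary.** Suppose the present rule ends at 10/50, with one such death replaced. If the death had been counted, the cohort would have closed at 50 without the replacement.

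- Replacement did not respond: still 10/50, p = 0.0245, success.
- Replacement responded: 9/50, p = P(X ≥ 9 | 50, 0.10) = 0.0245 + 0.0333 = 0.058, no success.

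If the 50 patients are exchangeable, the chance that the replacement is one of the ten responders is 10/50 = 20%.

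**The case against.** The plan is narrower in its exclusions, and more open about them, than a quick reading suggests.

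- A reader might infer that every early death not due to cancer is dropped. The documents do not support this. A toxic death falls reasonably under the toxicity route, since Protocol 5.2.1.1 treats discontinuation as ceasing treatment in any circumstances. SAP Table 10.2.1 does list death apart from "Treatment-related adverse event", but that table displays disposition and sets no evaluability rule. It is only a reason to be explicit.
- A reader might infer that the Table 10.1.1 footnote counts any early death and so contradicts SAP 4. The footnote is silent on cause. The footnote to Table 11.3.1.1 lists early death next to malignant disease, so shorthand is a fair reading. SAP 15.3 presents the Table 10.1.1 footnote as a clarification. Alignment is needed, but no direct contradiction is shown.
- The tests are defined on evaluable patients (Protocol 7.1 and 8.1), so the inflation is relative to treated patients, a target the plan did not choose for these cohorts in an exploratory trial.
- The All Treated sensitivity analysis (SAP 6.1) counts these deaths as non-responders. Listing 10.1.4 gives the reason for each non-evaluable patient and Listing 12.3.2.2 the cause of death.

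The first two points limit the claim as stated here. The third stands as a condition on the type I error figures, although the stated null gives no reason to prefer a population from which some certain non-responders have been removed. The fourth means the effect would be visible. It does not correct the primary result, the replacement rule or the decision counts.

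**Conclusion.** The gap is real but narrow: death before the first scan, after treatment, from a cause neither malignant nor treatment-related, or unknown. In the eight non-SCLC cohorts the primary ORR is then too high by the factor 1/(1−d) relative to treated patients. For the endometrial cohort the type I error passes 0.025 at each assumed rate. For the 25-patient rule it stays below 0.025 at 2% and 4% and just exceeds it at 8%. These sizes rest on assumed values of d and on the null holding among treated patients.

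Two stronger conclusions do not follow. The primary ORR in SCLC is not affected, because it uses All Treated. There the gap touches only replacement, the interim and decision counts, and the All Evaluable sensitivity analysis. Nor does one such death by itself overturn an endometrial success. Setting 10/50 against 10/51 would keep both the death and the replacement, and the plan would produce that count under neither rule. At the boundary the decision changes only when the replacement patient responded.

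**What to change.** In SAP 4 and Protocol 5.3, and in the synopsis entry that repeats 5.3, replace the malignant-disease death route with: *death from any cause after the start of the first infusion and before the first post-baseline tumor assessment*. State that these patients are treatment failures, evaluable, counted as non-responders and not replaced. This settles toxic deaths as well and takes the cause-of-death judgement out of the denominator.

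Exempt these patients from the SAP 4 condition of at least one complete infusion. Otherwise a death after a partial infusion would still be excluded. Align the Table 10.1.1 footnote with the new wording.

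The cost is a few sentences. No extra data or patients are needed. The downside is that ORR may come out slightly less favourable.
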